7.3. Lost to Follow-up

If a participant fails to return for study visits (and thus is considered lost to follow-up), study-site personnel must make all reasonable efforts to contact the participant to determine the participant's reason for discontinuation/withdrawal before considering the participant to be lost to follow-up. Such efforts should include repeated telephone calls, certified letters, email requests, etc. Measures taken to obtain follow-up information must be documented. Refer to Section 7.2, Participant Discontinuation/Withdrawal from the Study.

45

8. STUDY ASSESSMENTS AND PROCEDURES

Overview

The Schedule of Activities (Section 1.3) summarizes the frequency and timing of efficacy, PK, immunogenicity, biomarker, and safety measurements applicable to this study.

All PRO assessments should be conducted/completed before any tests, procedures, or other consultations, with the exception of a urine pregnancy test, to prevent influencing participant perceptions.

Blood collections for PK and biomarker assessments should be kept as close to the specified time as possible. Actual dates of all assessments will be recorded in the source documentation; in addition, times of all blood collections will be recorded in the source documentation (laboratory requisition form).

Additional serum or urine pregnancy tests may be performed, as determined necessary by the investigator or required by local regulation, to establish the absence of pregnancy at any time during the participation in the study. Results of all pregnancy testing should be documented in the participants' source documents.

Blood Sample Collection

The total blood volume to be collected from each participant through Week 48 of the study will be approximately 181.5 mL. In addition, repeat or unscheduled samples may be collected for safety reasons or for technical issues with the samples.

Sample Collection and Handling

The actual dates and times of sample collection must be recorded on the laboratory requisition form. Refer to the Schedule of Activities (Section 1.3) for the timing and frequency of all sample collections.

Instructions for the collection, handling, storage, and shipment of samples are found in the laboratory manual.

Study-Specific Materials

The investigator will be provided with the following supplies:

- Protocol
- Investigator's Brochure for guselkumab
- Site Investigational Product Binder
- Laboratory manual
- IWRS Manual
- Sample ICF

- PFS-U Instructions for Use
- Participant Study Participation Card
- Investigative Site File
- IV Ancillary Supplies
- Laboratory Kits
- Recruitment materials, as needed

8.1. Efficacy Assessments

Efficacy evaluations are consistent with those used to evaluate other therapies for HS and will include the following:

8.1.1. Hidradenitis Suppurativa Investigator's Global Assessment

The HS-IGA (Appendix 10 [Section 10.10]) documents the investigator's assessment of the participant's HS at a given timepoint. The anatomic region with the most severe HS activity at the baseline visit should be evaluated for erythema, drainage, and pain and/or tenderness to palpation for each participant. For each participant, the same anatomic site selected for evaluation at the baseline visit should be re-evaluated at each subsequent visit. The participant's HS is assessed as inactive (0), almost inactive (1), mild activity (2), moderate activity (3), or severe activity (4). A higher score indicates more severe disease.

8.1.2. Lesion Counts

Lesion counts are defined as the counting of abscesses, inflammatory nodules, non-inflammatory nodules, draining fistulas, and non-draining fistulas. Lesions will be counted during each visit.

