1.3. Schedule of Activities (SoA)

From Screening the	rough Week 48														
Period			Plac	ebo-Con	trolled P	eriod		Bli	nded Act	ive Treat	ment Per	riod		Safety Fo	ollow-up
Week	Screening ^a	0	2	4	8	12	16	20	24	28	32	36	40	44	48 or Early Termination Visit ^b
Study Procedures ^c				•	•			•	•		•	•		•	
Screening/Adminis	trative														
Informed consent	X														
Medical history and demographics	X														
Inclusion/ exclusion criteria	X	X													
Nicotine Use		X					X						X		
Alcohol Use		X					X						X		
Study Intervention	Administration	n													
Randomization		X					X ^d								
Study intervention IV administration ^e		X		X	X										
Study intervention SC administration ^e		X		X	X	X	X	X	X	X	X	X			
Safety Assessments															
Physical examination (including skin)	X														X
Vital signs	X	X	X	X	X	X	X	X	X	X	X	X	X	X	X
Waist Circumference		X													X
Tuberculosis evaluation	X	XX									X				
Columbia-Suicide Severity Rating Scale (C-SSRS) ^f	X	X	X	X	X	X	X	X	X	X	X	X	X	X	X
Chest radiograph	X														
12-lead ECG	X														

Period			Plac	ebo-Con	trolled Po	eriod		Bli	nded Act	ive Treat	ment Per	riod		Safety Fo	ollow-up
Week	Screening ^a	0	2	4	8	12	16	20	24	28	32	36	40	44	48 or Early Termination Visit ^b
Study Procedures ^c			I	l				I.		1					J
Urine pregnancy test ^g	X	X		X	X	X	X	X	X	X	X	X			X
Height		X													
Weight		X					X								X
Concomitant therapy		X													X
Adverse events		X													X
Efficacy Assessmen	its														
Hurley stage	X	X					X						X		
Lesion Counts	X	X	X	X	X	X	X	X	X	X	X	X	X	X	X
HS-IGA	X	X	X	X	X	X	X	X	X	X	X	X	X	X	X
DLQI ^f		X					X						X		
HADS ^f		X					X						X		
Hidradenitis Suppurativa Symptom Diary (HSSD) ^f		X	X	X	X	X	X						X		
Patient global impression of change (PGIC) of HS severity ^f			X	X			X						X		
Photographs of skin lesions ^h		X					X						X		
Clinical Laborator	y Assessment		•												
QuantiFERON®- TB test ⁱ	X														
Hepatitis B and C serology	X														
HIV antibody test	X														
Hematology	X	X					X						X		X

From Screening through Week 48															
Period		Placebo-Controlled Period					Blinded Active Treatment Period					Safety Follow-up			
Week	Screening ^a	0	2	4	8	12	16	20	24	28	32	36	40	44	48 or Early Termination Visit ^b
Study Procedures ^c															
Chemistry	X	X					X						X		X
Lipid panel ^j		X													
High sensitivity C- reactive protein (hs-CRP)		X		X			X						X		

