Pharmacokinetics a	nd Immunoge	nicity ^{k,l}													
Serum guselkumab concentration		X	X	X	X	X	X	X		X			X		X
Antibodies to guselkumab		X	X	X	X		X			X			X		X
Biomarkers															
Serum biomarkers ^c		X		X			X						X		X

Footnotes:

- a. The screening visit should occur no more than 4 weeks before the Week 0 visit.
- b. The Early Termination Visit should occur approximately 12 weeks after the last administration of study intervention (unless consent is withdrawn).
- c. All study procedures and evaluations are to be completed before study intervention is administered except where otherwise indicated.
- d. Randomization at Week 16 is for placebo group only and will not affect blinding.
- e. IV infusions and SC injections for Weeks 0, 4, 8 and SC injections for Weeks 12 through 36.
- f. The C-SSRS should be completed as the first assessment at screening after signing informed consent and before any tests, procedures, or other consultations, with the exception of the urine pregnancy test, and as the first assessment for baseline and all post-baseline visits, before any tests, procedures, or other consultations, with the exception of the urine pregnancy test, to prevent influencing participant perceptions. DLQI, HADS, HSSD, and PGIC should be performed before any tests, procedures, or other evaluations (Hurley stage, HS-IGA, Lesion counts), with the exception of the urine pregnancy test, for that visit.
- g. Women of childbearing potential must have a negative urine pregnancy test result before randomization and before receiving study intervention at all study intervention administration visits, and at Week 48 or early termination visit.
- h. Photographs to be taken at selected sites for participants who provide an additional consent; if such participants discontinue administration of study intervention early, however, photographs are not required at the final study visit.
- i. A tuberculin skin test is additionally required if the QuantiFERON®-TB test is not approved/registered in the country in which this study is being conducted.
- j. Participants must fast (ie, no food or beverages [except water]) for at least 8 hours before blood is drawn for lipid panel.

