5.1. Inclusion Criteria

Each potential participant must satisfy all of the following criteria to be enrolled in the study:

- 1. Be a man or a woman at least 18 years of age (or the legal age of consent in the jurisdiction in which the study is taking place).
- 2. Have moderate to severe HS for at least 1 year (365 days) prior to the baseline visit as determined by the investigator through patient interview and/or review of the medical history.
- 3. Have HS lesions present in at least 2 distinct anatomic areas (examples include but are not limited to left and right axilla; or left axilla and left inguinocrural fold).
- 4. Had an inadequate response to an adequate course of appropriate oral antibiotics for treatment of HS (or demonstrated intolerance to, or had a contraindication to, oral antibiotics for treatment of their HS) in the investigator's opinion.
- 5. Have stable HS for at least 1 month (28 days) prior to the screening visit as determined by the investigator through patient interview and/or review of the medical history.
- 6. Have a total abscess and inflammatory nodule (AN) count of ≥ 3 at the screening and baseline visit.
- 7. Must agree to daily use (throughout the entirety of the study) of one of the following over-the-counter treatments to the body areas affected with HS lesions: either soap and water, or a topical antiseptic wash containing chlorhexidine gluconate, triclosan, or benzoyl peroxide, or a dilute bleach bath.

- 8. Before randomization, a woman must be either:
 - Not of childbearing potential: premenarchal; postmenopausal (>45 years of age with amenorrhea for at least 12 months or any age with amenorrhea for at least 6 months and a serum follicle-stimulating hormone (FSH) level >40 IU/L); permanently sterilized (eg, tubal occlusion, hysterectomy, bilateral salpingectomy); or otherwise be incapable of pregnancy.

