2.7. Baseline and Endpoint

In general, the baseline measurement is defined as the closest measurement taken prior to or at the time of the first study agent administration date unless otherwise specified.

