5.4. Major Secondary Endpoints

There are 3 major secondary endpoints with 6 corresponding major secondary analyses. They will be performed in the order listed in Figure 2.

- The change from baseline in total AN count at Week 16.
- The change from baseline in DLQI at Week 16.

- The change from baseline in HS-related skin pain in the past 24 hours based on HSSD at Week 16.

This section outlines the definition and analyses of these major secondary endpoints. Data from all participants in FAS (Section 2.4.1.1) will be included and analyzed according to the randomized treatment groups.

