5.4.2. Analysis Methods

5.4.2.1. The Change from Baseline in Total AN Count at Week 16

For the change from baseline in AN count at Week 16, treatment comparisons will be performed using a Mixed-Effect Model Repeated Measures (MMRM) Model. The MMRM model will include baseline weight (≤ 95 kg, >95 kg), baseline Hurley stage status baseline values, visit, treatment group by visit interaction, and baseline value by visit interaction as explanatory factors.

The model will be performed based on all available data from the 3 treatment groups through Week 16. The treatment difference between a guselkumab group and the placebo group will be estimated by the difference in the least squares means (LSmeans). The 95% CIs for the differences in LSmeans and p-values will be calculated.

5.4.2.2. The Change from Baseline in DLQI at Week 16

The change from baseline in DLQI at Week 16 will be analyzed based on a mixed model (Section 5.2.3.3.2). under the assumption of missing at random (MAR). Marginal mean model will account for treatment group, baseline weight (≤ 95 kg, >95 kg), baseline Hurley stage status, baseline DLQI score, and AN count at each visit up to Week 16 through correlations among these variables. Marginal means will be compared between each of the guselkumab groups and placebo.

In addition, treatment differences and their associated 95% confidence intervals will be presented.

5.4.2.3. The Change from Baseline in HS-related Skin Pain in the Past 24 Hours Based on HSSD at Week 16.

The change from baseline in HS-related skin pain in the past 24 hours based on HSSD at Week 16 will be analyzed based on the analysis approach as specified in Section 5.4.2.1.

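### The AN-count model uses one of two scheduled pre-treatment AN counts; adding the screening count is a small, nearly free gain in precision, not the repair of an error.

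*Protocol*

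**What the plan says.** The lesion-count row of the Schedule of Activities (Protocol 1.3) begins "Lesion Counts X X X X"; those four columns are Screening and Weeks 0, 2 and 4. Protocol 8.1.2 agrees: "Lesions will be counted during each visit". Inclusion Criterion 6 makes both pre-treatment counts a condition of entry: "Have a total abscess and inflammatory nodule (AN) count of ≥ 3 at the screening and baseline visit". The gap between them is limited by a footnote to the Schedule: "The screening visit should occur no more than 4 weeks before the Week 0 visit".

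SAP 2.7 reduces these to one value: "the baseline measurement is defined as the closest measurement taken prior to or at the time of the first study agent administration date". For an eligible participant this is normally the Week 0 count.

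SAP 5.4 lists "The change from baseline in total AN count at Week 16" as a major secondary endpoint. Its model (SAP 5.4.2.1) contains weight category and then "baseline Hurley stage status baseline values, visit, treatment group by visit interaction, and baseline value by visit interaction as explanatory factors". On the data used, the SAP says: "The model will be performed based on all available data from the 3 treatment groups through Week 16". No efficacy model names the screening count. The SAP uses it only in the per-protocol check of Criterion 6 (SAP 2.4.1.2).

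**The concern.** A single lesion count carries counting error and visit-to-visit variation, so it measures a participant's usual level imperfectly. A second count taken before randomisation normally improves prediction of the Week 16 count. Adjusting for it narrows the confidence interval for the treatment contrast and does not alter the estimand, because it precedes treatment. The plan requires this count to be collected and then leaves it out of the model.

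At stake is precision on the AN-count comparison only. AN count is listed ahead of DLQI and pain among the major secondary endpoints, and the documents give no power, standard deviation or effect size for it. A reader therefore cannot tell how much margin that comparison has.

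**Working it through.** **The plan's own figure.** There is none for AN count. The only stated power is for HiSCR (Protocol 9.2 and SAP 1.4, Table 1). With 60 per arm, 25% versus 55% and two-sided 0.05, a pooled normal approximation gives 92.9% against the stated 93%. All six rows reproduce to within 2 points. That calculation does not involve the AN-count model.

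**Inputs from the documents.** 60 per arm; two pre-treatment counts up to 4 weeks apart; Week 16 outcome; one baseline covariate.

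**Inputs that must be assumed.** Three within-arm correlations: r (Screening with Week 0), ρ1 (Week 0 with Week 16) and ρ2 (Screening with Week 16), read as what remains after weight and Hurley stage. Week 16 data are treated as complete.

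**Formulas.** Given the Week 0 count, change and the Week 16 count have the same residual variance, so it is enough to work with the latter, scaled to variance 1.

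- Week 0 only: 1 − ρ1²
- Both counts: 1 − (ρ1² + ρ2² − 2·r·ρ1·ρ2)/(1 − r²)
- Equivalent sample size per arm: 60 divided by the ratio of the second to the first

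**Example.** With r = 0.7, ρ1 = 0.6, ρ2 = 0.55: the R² with both counts is (0.36 + 0.3025 − 0.462)/0.51 = 0.393, so residual variance is 0.607 against 0.640. The ratio is 0.948, and 60/0.948 = 63.3.

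| r | ρ1 | ρ2 | Ratio | Variance cut | Equivalent n per arm |
|---|---|---|---|---|---|
| 0.7 | 0.6 | 0.60 | 0.901 | 9.9% | 66.6 |
| 0.7 | 0.6 | 0.55 | 0.948 | 5.2% | 63.3 |
| 0.6 | 0.5 | 0.45 | 0.953 | 4.7% | 63.0 |
| 0.7 | 0.5 | 0.45 | 0.974 | 2.6% | 61.6 |
| 0.7 | 0.6 | 0.50 | 0.980 | 2.0% | 61.2 |
| 0.8 | 0.5 | 0.45 | 0.991 | 0.9% | 60.6 |
| 0.7 | 0.6 | 0.42 | 1.000 | 0% | 60.0 |

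The top row needs Screening to predict Week 16 as well as Week 0 does. The bottom row has ρ2 = r·ρ1 (0.7 × 0.6 = 0.42), meaning Screening adds nothing once Week 0 is known. The middle rows let correlation decay with time. For a comparison that starts at 80% power, a 2.0% cut gives 80.8% and a 5.2% cut gives 82.0%.

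**Check on counts.** Simulated Poisson counts restricted to AN ≥ 3 at both pre-treatment visits gave variance cuts of about 7% (stable level plus visit noise), 3% (stable level plus a decaying state) and 0.1% (decaying state only). These models are also assumptions.

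**Cost of the extra covariate.** For a two-arm comparison of 120, one more coefficient inflates variance by (120 − 5 − 2)/(120 − 6 − 2) = 113/112 = 1.009, about 0.9%. The cost should be somewhat less here, because the model is fitted to all three groups.

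**Effect of the treatment-failure rule.** SAP 5.2.3.2 sets treatment failures to their baseline value, so for them the analysed Week 16 count equals the Week 0 count. If a fraction f fail, with means and variances held equal, ρ1 becomes f + (1 − f)·0.6 and ρ2 becomes 0.7f + (1 − f)·0.6. In the top-row case, f = 10% gives 0.64 and 0.61 and a cut of 8.7%; f = 20% gives 0.68 and 0.62 and a cut of 7.6%.

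**The case against.** The strongest reply is that nothing here is wrong. A repeated-measures model adjusted for the Week 0 value, its visit interaction and both stratification factors is a standard, valid analysis. Which further covariates to include is a matter of preference. That stands, and a reader who infers a flawed test or an inflated type I error would be mistaken.

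The gain may also be very small. Screening can be up to 4 weeks older than Week 0. Prescription topicals are barred only in the 14 days before baseline, and systemic non-biologic therapy and oral antibiotics in the 4 weeks before it (Protocol 5.2), so some screening counts may be taken on, or just off, treatment. Selection on AN ≥ 3 at both visits and the treatment-failure rule work in the same direction. These points stand, and they are why the low single digits are the fair expectation.

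A reader might quote larger figures. Equal correlation at all three visits gives cuts of 11.1% at 0.5 and 17.0% at 0.7. That requires two counts at most 4 weeks apart to be no more alike than counts 16 weeks apart across treatment, and nothing in the documents supports it.

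The visit interaction adds a slope at each of five post-baseline visits, so the change is a little more than one term. With complete data, however, only the Week 16 slope bears on the Week 16 contrast, so the cost above is about right.

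Finally, a reader might infer that a missed AN result would end formal testing of DLQI and pain for that dose. The testing order is in Figure 2, which is not shown, and the consequence would also need a near-miss on AN count. It cannot be claimed from the text.

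**Conclusion.** This is a free improvement, not an error. Two pre-treatment AN counts are scheduled and required, and the model adjusts for one. Adding the other would cut the residual variance of the Week 16 AN contrast by 0 to about 10%, most plausibly 2-5%, or about 1-3 extra participants per arm of 60. About 1% must be set against that for degrees of freedom, so if Screening carries nothing beyond Week 0 the net effect is a loss of about 1%. The direction rests on lesion counts having visit-to-visit noise around a persistent level; the requirement for stable disease before screening (Criterion 5) fits such a level but does not establish it. The size rests wholly on assumed correlations.

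HiSCR, its Table 1 power, the estimand and the validity of the planned test are unaffected.

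**What to change.** In SAP 5.4.2.1, add the screening AN count and its interaction with visit as prespecified covariates beside the baseline value. Keep SAP 2.7 as it is, so that Week 0 remains the reference for change and for HiSCR. State how a missing screening count is handled, and what is done if the Week 0 count is missing, since SAP 2.7 would then make the screening count the baseline and the two covariates would coincide. For rescreened participants, name the screening period that led to randomisation.

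Make the change before the unblinding at the Week 16 database lock, by staff who have not seen the interim results.

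The matching change to the abscess, inflammatory-nodule and draining-fistula models (SAP 5.5.2.1) is optional: those endpoints carry nominal p-values only, and no gain has been worked out for them. DLQI and HSSD are not scheduled at Screening, so those endpoints have no screening value of their own to add.

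The cost is SAP wording and one covariate with its visit interaction in an existing model. No new data, visits or participants are needed.

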8.1.3. Hurley Staging

Hurley staging consists of 3 stages of disease that will be used to determine stratification:

- Stage I: Abscess formation, single or multiple, without sinus tracts and scarring
- Stage II: One or more widely separated recurrent abscesses with tract formation and scarring
- Stage III: Multiple interconnected tracts and abscesses across the entire area, with diffuse or near diffuse involvement

8.1.4. Hidradenitis Suppurativa Symptom Diary

The HSSD (Appendix 11 [Section 10.11]) is a 7-item patient self-reported questionnaire that assesses 5 HS-related symptoms including pain, tenderness, hot skin feeling, odor, and itchiness. The participants are asked to rate the severity of each symptom on a 0 to 10 numerical rating scale, with 0 indicating no symptom experience and 10 indicating the worst possible symptom experience. All 5 symptoms have a recall period of the past 7 days, except for 2 additional questions on pain which evaluate current pain and pain in the past 24 hours. Each individual symptom scale score, ranging from 0-10, will be summarized. A total symptom score, which will

also range from 0-10, will be derived by averaging the 5 individual scale scores that utilize the past 7-day recall period.

8.1.5. Dermatological Life Quality Index

The DLQI (Appendix 12 [Section 10.12]) is a dermatology-specific quality of life instrument designed to assess the impact of the disease on a participant's quality of life. It is a 10-item PRO questionnaire that, in addition to evaluating overall quality of life, can be used to assess 6 different aspects that may affect quality of life: symptoms and feelings, daily activities, leisure, work or school performance, personal relationships, and treatment. The DLQI produces a numeric score that can range from 0 to 30. A higher score indicates more severe disease.

8.1.6. Hospital Anxiety and Depression Scale

The HADS (Appendix 13 [Section 10.13]) consists of 2 subscales, one measuring anxiety (Ascale) and one measuring depression (D scale), which are scored separately. A higher score indicates more severe disease.

8.1.7. Patient Global Impression of Change of Hidradenitis Suppurativa Severity

The Patient Global Impression of Change (PGIC) of HS Severity (Appendix 14 [Section 10.14]) is a questionnaire that measures participants' perceived change (improvement or deterioration) in severity of their HS. Participants will rate how his/her HS has changed since the beginning of the study using a 7-point scale ranging from "a lot better now" to "a lot worse now" with a neutral center point ("neither better nor worse"). PGIC will be used as an anchor to test reliability and establish a clinical response criterion of other patient or physician reported outcomes for future reference.

